Monitoring of the progress of clinical investigations and the safety of participants: The proposed medication for this investigation is a commonly utilized substance for pain control. Patients will be monitored for adverse effects of these medications continuously while they are an inpatient. Please refer to Study Drug information and Informed Consent Appendix B for further details. The research team will work closely with the medical management team daily to note if any of these difficulties should arise. Other minor side effects will be recorded and monitored through chart review (nausea, abdominal pain, minor bruising and bleeding) at the conclusion of the inpatient admission. If necessary, blinding will be broken if any potential side effects are noted and the information regarding treatment would be helpful to the treating team. The clinical medical monitor of the investigation will be obtained with the help of CCTS and that person will be added to the study personnel. The PI will be blinded to the subject treatment arm, and thus limit bias in reporting.

Compliance:

The research team will meet monthly to discuss and review any of the above recorded events and report adverse events to the IRB accordingly. A yearly report will be filed with the IRB with regards to overall data safety. Study suspension/termination: In the event that there is a noted increase in the serious side effects of taking the study drug, the study will be suspended for review.

Data Accuracy:

The research team will meet monthly to go over the collected data and perform spot reviews to determine the accuracy of the data collection from the medical record and study procedures.

[Back to Top](#)

Future Use and Sharing of Material (e.g., Data/Specimens/Information)

If the material collected for this study will be used by members of the research team or shared with other researchers for future studies, please address the following:

- list the biological specimens and/or information that will be kept
- briefly describe the types, categories and/or purposes of the future research
- describe any risks of the additional use
- describe privacy/confidentiality protections that will be put into place
- describe the period of time specimens/information may be used
- describe procedures for sharing specimens/information with secondary researchers
- describe the process for, and limitations to, withdrawal of specimens/data

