Interventional Model Description: Compare the effectiveness of a NSAID to placebo in acute trauma setting.

Masking: Triple (Participant, Care Provider, Investigator)

Masking Description: Participant medical team will be blinded to the treatment or placebo intervention.

3. Outcome Measures

Primary Outcome: Length of Hospital Stay

Secondary Outcomes:

- Daily Concentrations of IL-1, IL-6, IL-10, and PGE2
- Incidence of Post-Traumatic Complications (e.g., bacterial pneumonia, SIRS, MODS, ARDS, and AKI)
- Mortality
- Visual Analogue Pain Scores
- Inpatient Morphine Milligram Equivalents
- Change in Inpatient Subjective Pain Reports
- Change in Outpatient Subjective Pain Reports

4. Background

Accidental trauma is the 4th leading cause of death in the United States, and it is associated with a complex inflammatory response. This response is associated with post-traumatic complications such as multi-organ dysfunction syndrome (MODS), bacterial pneumonia, acute respiratory distress syndrome (ARDS), systemic inflammatory response syndrome (SIRS), and post traumatic pain (PTP). It is unknown whether early modulation of inflammatory cytokines is associated with improved patient outcomes, reduced narcotic requirements, and improved patient subjective pain after hospital discharge.

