Data obtained at the UK during the study will be recorded and stored using password protected spreadsheet on the department's secure drive and will be maintained at the hospital by the research staff. Final analysis will be conducted using Excel spreadsheets. All documents will be stored on a password-protected research drive and only research personnel will have access to its content. Paper documents, including consent forms, will be stored in a locked cabinet in a secure research room in the Kentucky Clinic Suite K434.

All study personnel have completed human subject protection, responsible conduct of research, and patient confidentiality training. Only IRB-approved research personnel will administer consents and perform phone surveys. All efforts will be made to maintain the confidentiality of the patient reported data. Only study personnel listed in eIRB will have access to identified study data.

13. Provisions to Monitor the Data to Ensure the Safety of Subjects

Subjects in this study will be exposed to greater than minimal risk but presenting the prospect of direct benefit to individual in the study. The patients will be monitored continuously as inpatients post-operatively and any issues with medication effects, wound healing, or other medical complications will be logged as adverse events. Blinding will only be broken for unexpected complications potentially relating to ketorolac administration and the research study. The research team will meet monthly to monitor data collection and handling. During this time, study staff will also review adverse events logs.

14. Withdrawal of Subjects

We do not anticipate any situation in which a subject would be withdrawn from the study by the researchers should they wish to remain. We anticipate analyzing the data via an intention to treat analysis and thus would include data from all subjects initially enrolled, even if they developed an intolerance or medical contraindication to continuing the study.

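### The suspension rule turns on an increase in serious side effects of the study drug, but the available documents give no reviewer arm-level safety data and no reference rate, so an excess on ketorolac cannot be reliably told apart from a high background rate

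*Combined protocol and SAP*

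**What the plan says.** The IRB application, under Data and Safety Monitoring, contains the only suspension rule: if "there is a noted increase in the serious side effects of taking the study drug, the study will be suspended for review". It gives no event list, comparator, reference rate or threshold, and does not say who judges whether the rule is met.

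On review of events, the same section says: "The research team will meet monthly to discuss and review any of the above recorded events and report adverse events to the IRB accordingly". It adds a yearly report to the IRB on overall data safety, and says that inpatients are monitored continuously and that the team works daily with the medical management team. Protocol section 13 repeats the monthly meeting: "During this time, study staff will also review adverse events logs".

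On masking, the application says: "The PI will be blinded to the subject treatment arm, and thus limit bias in reporting". Protocol section 2 sets triple masking of participant, care provider and investigator.

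On an independent person: "The clinical medical monitor of the investigation will be obtained with the help of CCTS". The monitor's access to treatment codes and role in suspension are not stated.

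On unblinding single cases, the two texts differ. The application says "blinding will be broken if any potential side effects are noted and the information regarding treatment would be helpful to the treating team". Protocol section 13 says "Blinding will only be broken for unexpected complications potentially relating to ketorolac administration and the research study".

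**The concern.** The trigger is worded as an effect of the drug. To know that serious side effects of ketorolac have increased, someone must compare the ketorolac arm with the placebo arm, or compare the pooled rate with a trusted expected rate. The available documents provide for neither.

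Serious events unrelated to ketorolac are to be expected. Eligible patients have NISS above 9, and the listed secondary outcomes include pneumonia, SIRS, MODS, ARDS, AKI and mortality (protocol section 3). A masked team reading a log of such events cannot say from the count alone whether one arm is worse.

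A real excess on ketorolac could be put down to injury severity, or a run of unrelated complications could halt the study. If the team tried to settle the question from individual unblindings, it would erode its own masking. Protocol section 13 classes the study as greater than minimal risk, and for such research the application form requires an approved monitoring plan.

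**Working it through.** **The plan's own figures.** The suspension rule has no number to reproduce. The arm size used below comes from protocol section 6: SD 1.5 days, difference 0.928 days, alpha 0.05 and 80% power. A two-sided t-test with 42 per group has power 0.800, and 42 / (1 − 0.25) = 56 per group, 112 in total. Both stated figures reproduce.

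**Assumed inputs.** The documents give no serious-event rate for either arm. All rates below are assumptions for illustration.

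**Step 1: same total, different meaning.** Twelve serious events in 112 patients could be split in these ways:
- 11 ketorolac, 1 placebo: Fisher two-sided p = 0.004
- 6 and 6: p = 1.0
- 1 ketorolac, 11 placebo: p = 0.004 in the other direction

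The pooled count is the same in all three.

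**Step 2: a pooled rule.** Suppose the team had a rule based on an assumed 5% background. Take the smallest r with P(Bin(112, 0.05) ≥ r) ≤ 0.05. This gives r = 11, with tail probability 0.025. The chance of triggering is P(X + Y ≥ 11), with X ~ Bin(56, placebo rate) and Y ~ Bin(56, ketorolac rate):

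| Placebo | Ketorolac | Pooled rate | P(trigger) |
|---|---|---|---|
| 5% | 5% | 5% | 0.025 |
| 5% | 15% | 10% | 0.57 |
| 10% | 10% | 10% | 0.57 |
| 7.5% | 7.5% | 7.5% | 0.22 |
| 2.5% | 7.5% | 5% | 0.02 |

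The second and third rows are the point: 0.573 with a threefold excess and 0.571 with no drug effect. The last two rows show how far the rule depends on the assumed background. With no drug effect and a true background of 7.5%, it triggers 22% of the time. With a true background of 2.5% that ketorolac triples, it triggers 2% of the time.

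**Step 3: the same scenarios by arm.** Sum Bin(56, placebo rate) × Bin(56, ketorolac rate) over all pairs of counts whose one-sided Fisher p is at most 0.05. At 5% versus 15% the probability is 0.44. At 10% versus 10% it is 0.03. The by-arm comparison separates the two cases; the pooled rule does not.

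**Step 4: limits of by-arm counts.** Expected counts at 15% and 5% are 56 × 0.15 = 8.4 and 56 × 0.05 = 2.8, or 11.2 in 112 (10%). A split of 8 versus 3 gives Fisher two-sided p = 0.20, and monthly reviews before full enrolment would have fewer events.

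**The case against.** A reader might infer that the reviewers see only pooled events, that the medical monitor is denied by-arm data, and that the rule therefore cannot detect harm at all. The documents do not support that reading.

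- They do not say what the reviewers see. Pooled review is an inference from the masking of the PI and investigators; the masking of the other staff who read the logs is not stated.
- They are silent on the monitor's access, which is different from denying it.
- Single cases can be unblinded under either rule. Suspension is for review, and nothing says that review must be blinded.
- A pooled count can signal a large rise when the background is known. For 5% versus 15% with a known 5% background, the pooled rule triggers more often than the one-sided by-arm Fisher test (0.57 against 0.44). For 10% versus 30% with a known 10% background (rule: 18 or more), the figures are 0.89 and 0.80.
- Arm-level results were reachable: the continuation review reports a comparison of 35 with 35 patients and no apparent short-term adverse effects.
- An adverse event risk mitigation plan is listed among the attachments, but its text is not available.

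All of this stands, and it limits the point to what is set out here. It does not remove it. Pooled monitoring needs a reference rate, and none is given. The application ties case-level unblinding to the needs of the treating team, and neither rule provides for a comparison of arms. The 35-versus-35 report is not described as a planned safety review. It is also fair that adding by-arm counts alone would not complete the rule; the comparison it refers to must be stated as well.

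**Conclusion.** The point holds in a limited form. The suspension rule requires an increase to be attributed to ketorolac, and the available documents give no named reviewer the arm-level data and no reference rate with which to do so. As written, an excess on ketorolac cannot be reliably distinguished from a high background rate. That is weaker than saying harm cannot be detected.

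The size is illustrative only: the same pooled rule triggers with probability 0.57 under a threefold excess (15% versus 5%) and under no drug effect (10% in both arms). This rests on assumed rates, 56 per arm and complete follow-up for serious events. The unavailable risk mitigation plan may cover part of the gap.

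Separately, the two unblinding rules differ in scope. One covers any potential side effect where knowing the treatment would help the treating team; the other is restricted to unexpected complications potentially related to ketorolac. They must be reconciled; this review takes no position on which is right.

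**What to change.** In the application's Data and Safety Monitoring section and in protocol section 13:

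1. State that the medical monitor already planned is separate from the blinded team and takes no part in outcome assessment. For each monthly review, the monitor receives serious adverse event counts by arm from whoever holds the allocation code, and that holder should be named, since the documents do not say who it is.
2. State that the monitor tells the PI only whether the suspension rule is met.
3. State the comparison that the rule refers to: ketorolac versus placebo. No clinical threshold is proposed here.
4. Reconcile the two unblinding rules.
5. If the risk mitigation plan already provides any of this, refer to it in both places.

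The cost is one short table per monthly meeting, sent to a role already planned. One role becomes unblinded, and by-arm counts will often be inconclusive at this size (8 versus 3 gives p = 0.20). Their use is to show in which arm events occurred. IRB office comments of August 2023 in the application say that the study is closed to enrolment. The practical use now is to correct the plan, to report how safety was in fact reviewed, and to inform any successor trial.

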AddInfoProtocol	CCTS Full Research Proposal.pdf	CCTS Collaborative Grant-UK/Wake	1.233	smco282	7/24/2018 2:21:06 PM
StudyDrug	Ketorolac.pdf		0.466	bli255	2/26/2018 12:38:14 PM
StudyDrug	Form O - Inflammatory Markers.pdf		0.322	bli255	2/26/2018 12:38:03 PM
StudyDrug	Toradol.pdf	Toradol Prescribing Information	0.115	bli255	1/31/2018 1:25:48 PM

Protocol Changes

Protocol Number: 43611

[Click link to sort Changed Date](#)

Project Information **IsSubEnrollDataSpecimen** changed by jtgr238 on 8/7/2023 9:48:41 AM

YN

Project Information **ProjectEndDate** changed by jtgr238 on 8/7/2023 9:48:41 AM

8/10/2023 12:00:00 AM

Risk Level **RiskCategory** changed by jtgr238 on 8/7/2023 9:48:56 AM

21

Study Personnel Changes:

No Changes

There are no recorded changes to study personnel.

Protocol Type Comment by [name] - ORI to PI on 8/7/2023 9:25:12 AM

A few screening comments. Please see the following sections of the protocol for specifics:

- Project Information
- Risk Level
- Study Personnel

Additionally, as the study is closed to new enrollment, please remove the approved version of the informed consent as it will no longer be needed and thus does not need a new IRB approval stamp.

Project Information Comment by [name] - ORI to PI on 8/7/2023 9:18:59 AM

Please also update the anticipated end date of the research project.

Project Information Comment by [name] - ORI to PI on 8/7/2023 9:18:43 AM

As study is closed to new enrollment, please check "no" for "...will study be open to enrollment of new subjects..."

Risk Level Comment by [name] - ORI to PI on 8/7/2023 9:19:27 AM

As the study is closed to enrollment, please reduce the risk level to risk level 1: not greater than minimal risk.

Study Personnel Comment by [name] - ORI to PI on 8/7/2023 9:21:04 AM

[name]'s human subject protection training is set to expire in early September, 2023. While this may not affect the CR approval, they should plan to complete HSP refresher training as soon as possible to remain on the study. More information on HSP refresher training can be found at the following link: <https://www.research.uky.edu/office-research-integrity/three-year-refresher-hsp-training-faqs>

1. Title

Inflammatory Response to Trauma – Does Early Cytokine Modulation Improve Patient Outcome?

2. Study Design

Primary Purpose: Treatment

Allocation: Randomized

Interventional Mode: Parallel Assignment

Interventional Model Description: Compare the effectiveness of a NSAID to placebo in acute trauma setting.

Masking: Triple (Participant, Care Provider, Investigator)

Masking Description: Participant medical team will be blinded to the treatment or placebo intervention.

3. Outcome Measures

Primary Outcome: Length of Hospital Stay

Secondary Outcomes:

- Daily Concentrations of IL-1, IL-6, IL-10, and PGE2
- Incidence of Post-Traumatic Complications (e.g., bacterial pneumonia, SIRS, MODS, ARDS, and AKI)
- Mortality
- Visual Analogue Pain Scores
- Inpatient Morphine Milligram Equivalents
- Change in Inpatient Subjective Pain Reports
- Change in Outpatient Subjective Pain Reports

4. Background

Accidental trauma is the 4th leading cause of death in the United States, and it is associated with a complex inflammatory response. This response is associated with post-traumatic complications such as multi-organ dysfunction syndrome (MODS), bacterial pneumonia, acute respiratory distress syndrome (ARDS), systemic inflammatory response syndrome (SIRS), and post traumatic pain (PTP). It is unknown whether early modulation of inflammatory cytokines is associated with improved patient outcomes, reduced narcotic requirements, and improved patient subjective pain after hospital discharge.

Our preliminary data has shown: (1) elevated blood cytokine concentrations during the acute phase of trauma are correlated with the development of fatal post-traumatic complications, (2) that early administration of a non-steroidal anti-inflammatory drug (NSAID) resulted in decreased blood serum levels of IL-6, Prostaglandin E2 (PGE2), improved pulmonary edema, and enhanced arterioles ability to vasoconstrict in response to hemorrhage in animal models, and (3) that the addition of the internal physiologic parameters (inflammatory cytokines) to New Injury Severity Score (NISS – a marker of the external anatomical insult) significantly improves the ability to predict hospital length of stay of trauma patients when compared to NISS alone. Our group is the first to use an integrative approach that combines the external anatomic injury data with the internal physiologic response for accurate prediction of patient's clinical outcome. Therefore, if we apply this same mindset to treatment, we can improve the trauma patients' care by addressing both parameters as opposed to solely focusing on the external injury as done in the past. Our ability to modify post-traumatic physiologic response via short-term administration of a NSAID may lead to improved patient outcome.

Over the last decade, clinicians remain puzzled over the safety of NSAID administration after fracture in terms of bone union. In addition, given the current landscape for opioid epidemic in the United States, alternative non-opioid pain management during acute trauma has the potential to reduce opioid consumption and represents a pivotal component of multimodal analgesia strategy.

5. Inclusion and Exclusion Criteria

Inclusion Criteria

- Patient aged 18-75
 - a. Patient or legally authorized representative (LAR) able to provide consent.
 - b. Patient with New Injury Severity Score (NISS) > 9 at time of admission determined by trauma staff.
 - c. Anticipated admission \geq 5 days

Exclusion Criteria

- d. Patient age < 18 or > 75
- e. Patients with injury more than 24 hours prior to evaluation
- f. Hemorrhagic shock or risk of significant hemorrhage.
- g. Patients with preexisting inflammatory medical condition such as inflammatory arthropathy or inflammatory bowel disease
- h. Patients with acquired immunodeficiency syndrome (AIDS)
- i. Patients who are pregnant
- j. Patients with active GI bleed or ulceration
- k. Patients with chronic use of steroids or immune modulating drugs or history of organ transplantation
- l. Patients with preexisting chronic renal, liver, or lung disease
- m. Patients with history of myocardial infarctions
- n. Patients with chronic heart failure
- o. Patients with allergy to NSAID
- p. Patients with coagulation defects (e.g., clotting factor deficiencies, thrombophilia, or any bleeding disorder)
- q. Patients receiving chronic opioid therapy or treatment for opioid use disorder.

6. Sample Size Calculation

Pretrial sample size calculations were performed regarding LOS because this will be the primary outcome measure of the clinical trial. Using a significance level of 0.05 and an assumed SD of 1.5 days, a sample size of 42 patients per group (84 total) would yield 80% power to detect a difference of 0.928 days in average LOS between the placebo and ketorolac groups. Allowing for a dropout rate up to 25%, the target enrollment will be 112 patients total, with 56 patients per group. Power calculations were performed using nQuery 8.5 (Statistical Solutions Ltd; Cork, Ireland).

7. Statistical Analysis Plan

Group-level summary statistics will be calculated for demographic and clinical variables, and differences between the 2 groups will be evaluated using two-sample t-tests for quantitative measures and Fisher exact tests for categorical measures, as appropriate. LOS and MME values will be summarized using medians and interquartile ranges for each group. Group-level VAS pain scores will be summarized using means and standard deviations. An analysis of variance model will be fit to compare log-transformed LOS between the 2 groups. Linear mixed models will be used to estimate differences in VAS pain scores and log-transformed MME values over time between the 2 groups. Time and group comparisons for each cytokine will be made using linear mixed models, with and without adjusting for selected covariates. Patient demographic variables will be considered for inclusion as covariates in each model but will only be retained if they significantly improve the model. Linear mixed models may be log-transformed, double-log-transformed, or square-root-transformed to correct for right skewness, as appropriate. Likelihood ratio testing and Akaike information criterion will be used to select appropriate covariance structures in each case. A Kenward–Roger adjustment will be used to correct for negative bias in the standard errors and degrees of freedom calculations. Throughout the study, a P value of less than 0.05 will be considered significant. All analyses will be completed in SAS 9.4 (SAS Institute Inc.; Cary, NC).

8. Study-Wide Recruitment Methods

Potential patients will be prospectively identified either at the time of the initial consultation, at the morning fracture conference, based on the orthopaedic injury diagnosis (inclusion criteria noted above). Patients will be screened by their inclusion and exclusion criteria and will be considered for enrollment in the study should they meet study criteria.

9. Study Timeline

After arrival, patient screening and enrollment is expected within 12 hours of arrival to ensure initial blood draw. Further participation of subjects will include blood draws and ketorolac administration through day 5. Patient participation will continue through to their follow-up visits and conclude with their 6 weeks post discharge clinic visit. Detailed project timeline and schedule of activities is listed in Table 1.

Tentative time table of the proposed project												
Procedures	Enrollment	Inpatient						Outpatient				
		Day 1	Day 2	Day 3	Day 4	Day 5	Discharge	2 Week	6 Week	3 Month	6 Month	12 Month
Inclusion/Exclusion Review	X											
Informed Consent	X											
Blood Sample		X	X	X	X	X						
Ketorolac Intervention		X	X	X	X	X						
MME		X	X	X	X	X	X					
VAS		X	X	X	X	X	X	X	X	X	X	X
Post-Traumatic Complications		X	X	X	X	X	X	X	X	X	X	X

10. Procedures Involved

- Patient identification:** Patients will be identified on morning intake rounds by the trauma team and the research staff who are present daily to screen and enroll patients.
- Screening/Enrollment:** Study population will consist of 112 patients (56 control, 56 treatment) admitted to the inpatient surgical service at University of Kentucky (UK) level I trauma center for management of trauma care. Trauma patients that are between the ages of 18-75 and with NISS > 9 (moderate injury) with anticipated admission of ≥ 5 days (to ensure completion of the treatment) will be enrolled (Grisoni et al., 2001; Stevenson, Segui-Gomez, Lescohier, Di Scala, & McDonald-Smith, 2001). All patients will be initially treated according to the standard Advance Trauma Life Support (ATLS) protocol and standard ICU protocols (if applicable). Experienced clinical research staff will prospectively identify patients who meet the inclusion criteria and none of the exclusion criteria detailed in table 2.
- Randomization:** Consented patients will be randomized using a computer-generated algorithm to the control group (1-2 mL of intravenous saline every 6 hours for 5 days after admission) or treatment group (15 mg of intravenous ketorolac every 6 hours for 5 days after admission).
- Treatment:** Ketorolac (15 mg) has been chosen as the treatment of choice for several reasons:
 - Ketorolac has a similar pharmacodynamics profile as indomethacin, which was used

in our previous animal model (Xiang et al., 2012).

(2) It is readily available intravenously obviating limitations of oral intake.

(3) In numerous prospective clinical studies, ketorolac infusion produced no change in cardiac or hemodynamic parameters in patients undergoing major vascular surgery (Camu, Van Overberge, Bullingham, & Lloyd, 1990; Peirce, Fragen, & Pemberton, 1990).

(4) 30 mg is the approved dose that is consistent with United States Food and Drug Administration (FDA) labeling per the package

(5) Ketorolac is part of the routine trauma acute pain protocol

Patients with pre-existing medical co-morbidities and contraindications to ketorolac will be excluded from the study (see 5 for detailed exclusion criteria)

Patients in the treatment group will receive 15 mg IV ketorolac every 6 hours for 5 days after admission.

e. **Post-operative inpatient care:** Enrolled patients will have daily blood samples (10 cc) will be collected post-admission and at 24 hours intervals for 5 days by blinded health care personnel. The initial blood sample will be collected within 12 hours of initial injury and before the first scheduled administration of ketorolac to establish baseline cytokine profile. Subsequent blood sample collection will be 24 hours apart. Medication compliance and monitoring will be performed daily by the same research coordinators.

Sandwich ELISA will be used to determine the concentrations of IL-1, IL-6, IL-10, and PGE2 in obtained blood samples. Blinded quality control samples will be included in every batch for each ELISA assay. This will allow for the calculation of coefficient of variation (CV) within and across patient cohorts. In the present study, the CV will be calculated for IL-1, IL-6, IL-10, and PGE2. If wide variations are observed among the analytes during the analysis, we will restrict our analysis to analytes in which the CV is less than 20%.

In addition to the standard trauma labs (Sodium, Potassium, Creatinine, Lactic acid, Glucose, Platelet, blood urea nitrogen (BUN), hematocrit, and white blood cell count), patient demographics (sex, age, and BMI), injury data (mechanism of injury, NISS, and types of surgical/procedural interventions), posttraumatic complications (occurrence of bacterial pneumonia, ARDS, SIRS, MODS), complications defined in the National Trauma Dataset, and inflammatory data will be collected. This data will be maintained in our clinical database (REDCap) by a full-time Clinical Study Coordinator.

Enrolled patients will be monitored daily by research staff throughout their hospital stay and routine outpatient clinic visits. Patient's subjective pain scores will be assessed and documented by the trained nursing staff using Visual Analogue Scale (VAS) daily. Pre-injury narcotics use along with other pain modulating medication intake will be recorded per day in morphine milligram equivalent (MME) for the duration of ketorolac or placebo therapy in our password protected database. Patients' clinical course will be monitored closely and daily by research staff to ensure no NSAIDs will be administered to the control cohort to ensure consistency and protocol adherence. After patient discharge, various patient surveys will be used to assess patient pain, function, and quality of life. Opioid and pain modulating medication prescription refills will be monitored using State Scheduled Prescription Electronic Reporting System. Patient narcotic requirement will be assessed during all the routine follow up visits by the same research staff to maintain consistency.

11. Data and Specimen Banking

Blood sample specimens obtained from the research subjects will be labeled with the patient's unique study ID number and will be stored in the CCTS lab until analysis. Following analysis, the specimens will be disposed of in accordance with UK policies. No specimens will be retained for future studies. The stored de-identified data from the study will be kept for a minimum of 6 years for records in the event follow-up studies are pursued and will remain protected and encrypted. Data will be permanently

deleted following this time period. The banked data will be stored on a password-protected research drive. Upon conclusion of the study, the data will be stored in a password encrypted file that only the PI has access to.

12. Data Management

Following initial enrollment, each patient will be assigned a unique patient identifier. All electronic documentation containing total morphine equivalents, specimen results, and all other medical information will be associated with this unique patient identifier during analysis. All protected health information will be stored in a separate, password-protected research file that will not be accessed regularly. Following our secondary analysis, all personal health information will be removed from our electronic files and destroyed in accordance with patient privacy guidelines.

Data obtained at the UK during the study will be recorded and stored using password protected spreadsheet on the department's secure drive and will be maintained at the hospital by the research staff. Final analysis will be conducted using Excel spreadsheets. All documents will be stored on a password-protected research drive and only research personnel will have access to its content. Paper documents, including consent forms, will be stored in a locked cabinet in a secure research room in the Kentucky Clinic Suite K434.

All study personnel have completed human subject protection, responsible conduct of research, and patient confidentiality training. Only IRB-approved research personnel will administer consents and perform phone surveys. All efforts will be made to maintain the confidentiality of the patient reported data. Only study personnel listed in eIRB will have access to identified study data.

13. Provisions to Monitor the Data to Ensure the Safety of Subjects

Subjects in this study will be exposed to greater than minimal risk but presenting the prospect of direct benefit to individual in the study. The patients will be monitored continuously as inpatients post-operatively and any issues with medication effects, wound healing, or other medical complications will be logged as adverse events. Blinding will only be broken for unexpected complications potentially relating to ketorolac administration and the research study. The research team will meet monthly to monitor data collection and handling. During this time, study staff will also review adverse events logs.

14. Withdrawal of Subjects

We do not anticipate any situation in which a subject would be withdrawn from the study by the researchers should they wish to remain. We anticipate analyzing the data via an intention to treat analysis and thus would include data from all subjects initially enrolled, even if they developed an intolerance or medical contraindication to continuing the study.

However, a subject may choose to withdraw from the study on their own accord, at any time, for any reason. Contact information and instructions detailing how to withdraw from the study will be provided in the consent form and will involve contacting the principal investigator directly. If a subject chooses to withdraw, any and all data that was previously collected will be included in the analysis; however, we will cease any further data collection. All personal health information collected prior to a patient's withdrawal from the study will be destroyed in accordance with patient privacy laws. In addition, any paper documents obtained will be destroyed in accordance with standard HIPPA guidelines. Upon being notified of a patient's decision to withdraw from the study, researchers will no longer contact the patient via phone, administer in-office surveys, or access their medical information online.

15. Risks to Subjects

Long-term non-steroidal anti-inflammatory drug (NSAID) intake has been correlated with impaired or delayed fracture healing in animal and clinical studies with a dose dependent response. However, the evidence in animal studies is conflicting, and there are few retrospective clinical studies and even fewer large scale prospective randomized trials. A recent meta-analysis demonstrated that higher quality studies found no evidence of negative effect of NSAIDs on bone-healing. To our knowledge, the present study will be the largest prospective randomized clinical trial to evaluate the effect of short term and low dose administration of NSAID on trauma patient outcomes, opioid consumption, and fracture union rates.

Surgical risks are described to the patient prior to surgery and are part of standard of care procedures for hip fracture surgery. There are no additional surgical risks to patients who participate in this study.

Although the treatment arm in this study involves randomization to ketorolac, standard ketorolac is commonly used as part of the acute trauma pain protocol. Risks commonly associated with ketorolac are listed in attachments to the eIRB.

There is also a risk of a breach of confidentiality. All research team members are appropriately trained and understand the importance of confidentiality.

16. Potential Benefits to Subjects

The use of ketorolac in the acute period could potentially decreasing the inflammatory cascade leading to a decrease in severe posttraumatic complications such as multi-organ dysfunction syndrome, bacterial pneumonia, acute respiratory distress syndrome, systemic inflammatory response syndrome, and post traumatic pain. Additionally this could result in decreased ICU stay and better postoperative pain control (decreasing opioid dependence/usage).

17. Vulnerable Populations

At high energy trauma centers such as those participating in the study, some percentage of the patients will be eligible for the study but will not be able to consent due to traumatic brain injuries, or for other reasons related to their injury. We will consent these patients using the individuals' legally authorized representative. The process for obtaining consent for surgery or study participation varies based upon the state the patient is being treated within, and as such the details of this process will be guided by the standard practice of the local IRB.

Whenever possible, we will also discuss involvement in the study with the patient's family (provided the patient gives permission for us to discuss with them) to ensure that the decision to participate in the study is made with appropriate consideration and that the entire family is comfortable with involvement.

18. Sharing of Results with Subjects

To maintain the blinded nature of the study, the subjects will not be aware of which treatment group a subject has been randomly assigned to. At the conclusion of the study, following de-identification and data analysis, results of this data collection may be shared with patients who have participated in this research as it becomes available, if they request it verbally or in writing. This will only occur after final data analysis if a subject inquires.

19. Setting

Research subjects will be identified, recruited, and followed post-operatively as inpatients at the

University of Kentucky Chandler Hospital. They will be followed post-discharge at the Kentucky Clinic. Data analysis will primarily occur in locked, private offices at in one of two secure research offices located at the Kentucky Clinic.

20. Resources Available

